Summary of Trial Design	A two-stage open-label, single arm phase I/IIa trial of carbamazepine in children with skeletal dysplasia who are outpatients. The trial includes an initial dose determination stage (Stage 1) followed by long-term assessment of efficacy and safety at the chosen dose (Stage 2).			
Summary of Participant Population	Children with a diagnosis of Metaphyseal chondrodysplasia, type Schmid (MCDS) with confirmed COL10A1 pathogenic mutation.			
Planned Sample Size	40 participants (11 participants Stage 1 dose titration; 29 participants Stage 2 treatment)			
Baseline Observation Duration	Stage 1 participants: 12-18 months (dependent on covid-19 impact)Stage 2 participants : 6 months			
Treatment Duration	Stage 1 participants: 24 months + additional optional 12 months*			
	Stage 2 participants: 12 months*			
	*LPLV must occur no later than 31 st January 2024			
Planned Trial Period	70 months			
	Objectives	Outcome Measures		
STAGE 1 – DOSE TITRATIO	N & TOLERABILITY			
Primary	To assess the safety and tolerability of carbamazepine (CBZ) in the treatment of children with MCDS who are ambulant but have not yet reached skeletal maturity (open epiphyses)	Laboratory safety assessments, adverse events and physical examinations collected post IMP administration.		
	To determine an appropriate dose of CBZ to inform the treatment of children with metaphyseal chondrodysplasia, type Schmid in Stage 2.	Outcome of dose-titration safety review at 6 months post IMP treatment initiation.		
Secondary	To evaluate the effect of CBZ on pain in children with MCDS over 24 months	 Alteration from baseline in pain perception over 24 months as measured by: PEDSQL Pain Coping Inventory PEDSQL Pain Questionnaire 		

STAGE 2 – TREATMENT			
Primary	To evaluate efficacy of CBZ for the treatment of children with MCDS who are ambulant but have not yet reached skeletal maturity (open epiphyses)	Alteration from baseline in growth velocity over 12 months	
	To determine if efficacy of CBZ warrants a subsequent formal development programme for carbamazepine in this indication	Growth velocity follow-up data at 12 months post treatment initiation	
Secondary	To evaluate the effect of CBZ on height in children with MCDS over 12 months	Alteration from baseline in height percentile over 12months	

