5.2 Stage 1 (UK only) – Dose titration and tolerability & treatment

Stage 1 is a dose titration of carbamazepine in 5mg/kg increments to a preselected maximum dose of 20mg/kg, with review of safety and tolerability in a population of 11 participants from two UK trial sites over a 12 month period (See Table 6). A safety review will be conducted, once the 11th patient has reached the 6 month time point. For a detailed description of the Stage 1 dose titration, see section 8.8. Once a suitable dose is agreed, Stage 1 participants will continue CBZ treatment at this agreed dose until they reach 24 months treatment (See Table 7). There will also be an opportunity to continue CBZ treatment for an additional 12 months for participants who wish to do so. This optional CBZ treatment will be a subject to an additional informed consent at visit 2.5. Their 12/24 month data will be included in the final analysis following Stage 2, subject to IDMC consultation.

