5.3 Stage 2 - Treatment

During Stage 1, the additional 29 Stage 2 participants will be recruited and will commence the 6-month observation period in preparation for the start of Stage 2. Stage 2 is a 12-month CBZ treatment stage in a population of 29 participants from multiple trial sites across the UK, and self sponsored trial sites across Europe and Australia(See Table 3. Stage 2 patients will only begin treatment after the Stage 1 safety review is completed and when an agreed safe and tolerable dose has been identified (section 8.8.6). In the case that the dosing regimen remains the same, Stage 1 participants will be included in Stage 2 analysis. In the case that the dosing regimen changes, the IDMC will be consulted about whether inclusion is appropriate. Participants who are in the Stage 2 treatment phase may be on a lower dosing regimen if they are unable to tolerate the maximum dose of 20mg/kg. The titration will need to be recorded in the patient's notes and documented in the trial MACRO database. Clinical judgement alongside clinical assessments will be used to determine if the dose must be lowered.

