2.4 Definition of outcome measures

2.4.1.1 Primary objectives/endpoints

	Objective	Outcome
Primary	To evaluate efficacy of CBZ for the treatment of children with MCDS who are ambulant but have not yet reached skeletal maturity (open epiphyses)	Alteration from baseline in growth velocity over 12 months
	To determine if the level of efficacy warrants a subsequent formal development programme for CBZ in this indication.	Growth velocity follow-up data at 12 months post treatment initiation

Participants undergo an observational phase (12-18 months for Stage 1 participants; 6 months for Stage 2 participants) prior to starting treatment. Measurements taken include data on height and weight. The same measurements are taken at various time points during the treatment period, allowing an assessment of growth velocity and any change which might be due to treatment.

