2.7 Overview of MCDS-Therapy Clinical Trial (from Protocol)

*The 12 month baseline observational visit may be rescheduled to a 18 month visit for participants who have missed the 12 month visit due to COVID-19 (Stage 1 UK participants only).

[^] To aid with study participant retention due to COVID 19, with discussion with the CI, the 12 month baseline observational visit window can be up to 12 months and 8 weeks. This will be assessed on a case by case basis through discussion with the site PI^a with approval from the CI and the NCTU team notified.

Eligible Stage 1 participants may continue treatment for further 12 months (up to 36 months) subject to a separate informed consent at visit 2.5.

Last Patient Last Visits in Stage 1 and Stage 2 must be completed by 31st January 2024.

3 Study Population

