3.1.5 Baseline characteristics

Demographic, clinical and surgical characteristics recorded at the first visit during the baseline observation period will be summarised. Categorical data will be presented as frequencies and percentages, continuous data will be presented as number of patients, mean, median, standard deviation, minimum, maximum and range.

Demographic characteristics: age, sex, height (or length if <2 years old), sitting height in children >=5 years old, crown-rump length (CRL) in children <5 years old.

Clinical characteristics: age at onset of first symptoms, pain at diagnosis of MCDS (yes/no), current frequency of pain, joints affected with pain, surgical interventions to manage MCDS symptoms (yes/no), bone age, head/neck of femur angle.

Example Table: Patient demographics at baseline

	n=X	
Sex		
Male		
Female		
Age (years)		
Median		
Mean		
Median BMI		
Blood pressure (mmHg)		
Systolic		
Diastolic		

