4.3.3 Secondary analysis of primary outcome

4.3.3.1 Surgical interventions

Surgical interventions are recorded throughout the baseline and treatment periods for all participants. Following completion of the trial a review will be conducted by the CI to assess whether any of the surgical interventions could have the potential to affect growth. In the event that some interventions are thought to have potentially affected growth, the primary analysis will be repeated using an extension to the primary analysis model which allows the growth rate to change following surgery.

Let δ_{ij} be an indicator variable taking the value 0 for measurements observed before time T_i^* and 1 for measurements observed after time T_i^* , where T_i^* denotes the time of the surgical intervention for participant *i*.

The model used to adjust for surgical interventions is then given by:

$$y_{ij} = \beta_1 + \beta_2 t_{ij} + \beta_3 \tau_{ij} (t_{ij} - T_i) + \beta_4 \delta_{ij} (t_{ij} - T_i^*) + \varepsilon_{ij}$$

Before the surgical intervention the model remains unchanged from the model used in the primary analysis, however after the surgical intervention, the model becomes

$$y_{ij} = (\beta_1 - \beta_4 T_i^*) + (\beta_2 + \beta_4)t_{ij} + \beta_3 \tau_{ij} (t_{ij} - T_i) + \varepsilon_{ij}$$

and so allows for a change in growth rate from the point of surgery onwards. The change in growth rate is estimated by the parameter β_4 .

4.3.3.2 25-OH Vitamin D

25-OH vitamin D levels might predict secondary effects on bone health and could be considered a potential confounding variable. Bone biochemistry bloods (25-OHD vitamin D [nmol/L]) are recorded 6 monthly throughout the trial. 25-OH vitamin D levels will be included as a time-varying covariate in the primary analysis model to adjust for any effects of vitamin D level. A last observation carried forward approach will be taken to impute vitamin D levels when missing.

Let z_{ij} be the standardised 25-OH vitamin D level for participant *i* at time t_{ij} (j = 1,..., n_i),

i.e. $z_{ij} = (x_{ij} - \bar{x})/\sigma_x^2$, where x_{ij} is the observed 25-OH vitamin D level, and \bar{x} and σ_x^2 are the sample mean and variance of all 25-OH vitamin D observations across all participants.

The model used to adjust for the effect of vitamin D is given by:

$$y_{ij} = \beta_1 + \beta_2 t_{ij} + \beta_3 \tau_{ij} (t_{ij} - T_i) + \beta_4 z_{ij} t_{ij} + \varepsilon_{ij}.$$

This can be written as:

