4.4.3 Additional secondary analyses

Use of surgical interventions to manage the condition will be captured on the eCRF over the whole follow up period. These will be reported descriptively as the type and proportion of participants experiencing an event per three month period from baseline until the end of trial follow up.

5 Safety

Laboratory safety assessments outside the appropriate local normal reference range will be reported at a participant level. Abnormal physical examinations will be reported at a participant level together with any further details provided.

All AEs occurring from the point of consent to the end of trial participation are recorded in the trial MACRO database eCRF. AEs are assessed for their relationship to treatment and coded as: Unrelated, Unlikely, Possible, Probable, Definitely, or Not assessable. Severity is graded according to the Common Terminology Criteria for Adverse Events (CTCAE), Version 5.0, Published: November 27, 2017.

Grading is based on the following general guideline:

- **Grade 1 Mild**; asymptomatic or mild symptoms; clinical or diagnostic observations only; intervention not indicated.
- **Grade 2 Moderate**; minimal, local, or non-invasive intervention indicated; limiting age-appropriate instrumental Activities of Daily Living (ADL).
- **Grade 3 Severe** or medically significant but not immediately life-threatening; hospitalization or prolongation of hospitalization indicated; disabling; limiting self-care ADL.
- Grade 4 Life-threatening consequences; urgent intervention indicated.
- Grade 5 Death related to AE.

AEs are coded using the Medical Dictionary for Regulatory Activities (MedDRA) version 22.0. The Clinical Data Management System (CDMS) auto-codes the majority of AEs to the latest version of the MedDRA dictionary. If this is not possible, AEs are coded from the MedDRA dictionary by the Cl.

SARs occurring from the first participant's dose of IMP to the last participant's end of follow-up are recorded on the trial MACRO database eCRF. Following this defined active monitoring period for SARs, investigators are still required to report any SARs or SUSARs which are brought to their attention.

For each SAE the following information is collected:

- 1. Full details in medical terms and case description
- 2. Event duration (start and end dates, if applicable)
- 3. Action taken
- 4. Outcome
- 5. Seriousness criteria
- 6. Causality in the opinion of the investigator

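### SAP 4.4.3 tabulates surgery by time from baseline without separating untreated from treated time, so a change over periods cannot be attributed to carbamazepine

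*SAP*

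**What the plan says.** SAP 4.4.3 gives surgery one descriptive summary over time: the type of intervention and the "proportion of participants experiencing an event per three month period from baseline until the end of trial follow up". Protocol 11.2.2 has the same rule. Neither text names a denominator, and neither splits the table by treatment status or by stage. SAP 2.1 pools the stages for the Stage 2 analysis because the dose regimen was unchanged.

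The stages run on different clocks. SAP 2.4.1.1: "Participants undergo an observational phase (12-18 months for Stage 1 participants; 6 months for Stage 2 participants) prior to starting treatment". Protocol 5.3: "Stage 2 is a 12-month CBZ treatment stage in a population of 29 participants". Protocol 5.2: "Stage 1 participants will continue CBZ treatment at this agreed dose until they reach 24 months treatment". SAP 2.7 adds an optional further 12 months for eligible Stage 1 children.

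SAP 4.4.3 does not define baseline. Two other sections point to the start of observation. SAP 3.1.5 says "Demographic, clinical and surgical characteristics recorded at the first visit during the baseline observation period will be summarised", and SAP 4.3.3.1 says "Surgical interventions are recorded throughout the baseline and treatment periods for all participants".

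**The concern.** Protocol section 3 explains why untreated data are collected: so that each child can be compared before and after starting carbamazepine. A table on months from baseline cannot make that comparison wherever one period holds children on both sides of their treatment start. The group observed also changes, because Stage 2 children finish much sooner than Stage 1 children.

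The rest of the SAP avoids this. The growth model (4.3.1) and the secondary outcome model (4.4.2) use each child's own treatment start, T_i, and the plots in 4.4.1 mark baseline and treatment visits. The surgery table is the exception.

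What is at stake is how the table is read. Protocol section 12 asks whether carbamazepine is cost-effective against surgical and pain management alone, and it names health-service use in the trial as one data source. A reader could take a rise or fall across the periods as evidence on that question.

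**Working it through.** **Plan's own figure.** Stage 1 plus Stage 2 is 11 + 29 = 40, as stated in the Protocol synopsis and SAP 2.6. There is no power calculation to reproduce, since the sample size rests on feasibility.

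**Inputs.**
- Stage 1: n = 11, untreated 12 months (up to 18), then 24 months of treatment, optionally 36.
- Stage 2: n = 29, untreated 6 months, then 12 months of treatment.
- Not given in the documents: how many Stage 1 baselines last 18 months (0, 5 and 11 assumed), and how many children enter the extension (0 to 11 assumed). No dropout is assumed.

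**Step 1: planned treatment time, in months from the first observation visit.**
- Stage 2: 6 to 6 + 12 = 18.
- Stage 1, 12-month baseline: 12 to 12 + 24 = 36, or 48 with the extension.
- Stage 1, 18-month baseline: 18 to 18 + 24 = 42, or 54 with the extension.

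**Step 2: children untreated / treated in each span.**

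| Months from baseline | No 18-month baselines | Five | All eleven |
|---|---|---|---|
| 0-6 | 40 / 0 | 40 / 0 | 40 / 0 |
| 6-12 | 11 / 29 | 11 / 29 | 11 / 29 |
| 12-18 | 0 / 40 | 5 / 35 | 11 / 29 |
| 18-36 | 0 / 11 | 0 / 11 | 0 / 11 |
| 36-42 | 0 / (0 to 11) | 0 / (5 to 11) | 0 / 11 |
| 42-48 | 0 / (0 to 11) | 0 / (0 to 11) | 0 / (0 to 11) |
| 48-54 | none | 0 / (0 to 5) | 0 / (0 to 11) |

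In months 6-12 the treated share is 29/40 = 72.5%. Without 18-month baselines, 2 of 12 three-month periods are mixed (2 of 16 with the extension). With some or all at 18 months, 4 of 14 are mixed (4 of 18 with the extension). At month 18 the number observed falls from 40 to 11, all of them Stage 1 UK children.

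**Step 3: what the fall to 11 can do with no drug effect (assumed risks, for illustration).**
- Equal risk of 5% per quarter in both stages, denominator the children observed: the proportion stays at 5%.
- Same risk, denominator held at 40: after month 18 it reads 0.05 × 11/40 = 1.4%. With assumed risks of 2% and 10% it reads 0.55% and 2.75%.
- Stage 1 at 5% and Stage 2 at 2%, denominator the children observed: (11 × 0.05 + 29 × 0.02)/40 = 2.8% up to month 18, then 5%. Reversed: (11 × 0.02 + 29 × 0.05)/40 = 4.2%, then 2%.

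**Step 4: the same children counted from T_i.**

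| Months from treatment start | Children |
|---|---|
| -18 to -12 | 0 to 11 |
| -12 to -6 | 11 |
| -6 to 0 | 40 |
| 0 to 12 | 40 |
| 12 to 24 | 11 |
| 24 to 36 | 0 to 11 |

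No period is mixed. The span from -6 to 12 is planned for every child and gives 40 × 6/12 = 20 untreated and 40 × 12/12 = 40 treated person-years. The fall to 11 remains, now at month 12, so numbers under observation and a split by stage are still needed.

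**The case against.** The strongest reply is that little hangs on this table. Surgery is in neither the Protocol's outcome table nor the SAP's secondary endpoints. No test or decision rule uses it, and the text promises description only. This stands, and it limits the severity.

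Nor is the table the only account of surgery, though a reader might infer that. SAP 3.1.5 summarises prior surgery, and 4.3.3.1 provides a chief investigator review with a surgery-adjusted growth model if needed. Surgery is recorded as an adverse event, so it enters the by-participant listing in 5.1.1, and serious events appear with onset date in 5.1.2. With at most 40 children, much could be reconstructed. The health economic model has its own analysis plan, and Protocol 13.3 releases electronic trial data to the health economist, so the model need not depend on this table. All of this stands, but none of these outputs gives a rate before and on treatment.

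Baseline could also mean treatment start. Then no period would be mixed, but surgery before treatment would be left out and the fall to 11 would come after month 12. The wording would still need clarifying.

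Finally, a before/on comparison has a weakness of its own. Eligibility is re-assessed before treatment, and planned surgery can exclude a child (Protocol 7.2), so the two rates could differ through selection alone. This stands and belongs in the label of any such summary.

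**Conclusion.** The point holds as a minor one. The stated time axis combines treated and untreated children in months 6-12, and up to month 18 where Stage 1 baselines are long. After month 18 it describes Stage 1 children only. A change over periods therefore cannot be attributed to carbamazepine.

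Three stronger readings are tempting, and the documents do not support them:
- That every period is mixed. Months 0-6 are wholly untreated, and periods after month 18 are wholly treated.
- That any trend reflects the schedule rather than the drug. The table cannot tell the two apart, which is a weaker statement. With the children observed as denominator and equal risk in both stages, the shrinking sample creates no trend.
- That later rates will be understated 3.6-fold (40/11). This needs 40 to be kept as the denominator throughout, which the SAP does not say. The defect is that no denominator is named.

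The conclusion assumes that baseline means the start of observation, that planned durations are kept, and that no child drops out. Visit windows, the three-month eligibility re-assessment (Protocol 7.2) and final visits brought forward (Protocol 8.12) can shift the limits for single children without changing the overall pattern.

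**What to change.** In SAP 4.4.3:
- Count the three-month periods from each child's own start of carbamazepine (T_i), negative before and positive after.
- Use the children under observation in each period as denominator, show that number, and present Stage 1 and Stage 2 separately.
- Add events per person-year for months -6 to 0 and 0 to 12, labelled descriptive. Note that the eligibility re-assessment before treatment, including planned surgery, may select children, and that withdrawals or visits brought forward can shorten the window.
- If the from-baseline table stays, define baseline and print the number at risk for each period.

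The cost is SAP wording and a table layout. No new data are needed: surgery is already recorded through both periods, T_i is used in the growth model, and the surgery-adjusted model already requires the time of surgery.

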5.1.1 Adverse events

The number of adverse events and adverse reactions (those possibly, probably or definitely related to treatment) and the worst grade AE and AR per participant will be summarised descriptively.

Example table: Number of events per participant

	Mean (SD)	Median (Q1, Q3)	Min, Max
All adverse events			
Adverse reactions (possibly, probably, definitely)			

Example table: Worst grade reported per participant (number, %)

	None	Mild	Moderate	Severe
All adverse events				
Adverse reactions (possibly, probably, definitely)				

The number of participants reporting each type of adverse event (by MedDRA System Organ Class) will be tabulated.

Example table: Number and percentage of participants affected by each adverse event, reported by System Organ Class

Event term		Total		Mild		Moderate		Severe	
	Ν	%	Ν	%	Ν	%	Ν	%	
Blood and lymphatic system disorders									
Cardiac disorders									
Endocrine disorders									
Eye disorders									
Gastrointestinal disorders									
General disorders and administration site conditions									
Immune system disorders									
Infections and infestations									
Injury, poisoning and procedural complications									
Investigations									
Metabolism and nutrition disorders									

The number and percentage of patients experiencing at least one high grade event (grade 3/4/5).

A line listing of all AEs will be reported, by participant, including severity, seriousness and relationship to study treatment.

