10 PHARMACOVIGILANCE

10.1 Definitions

Term	Definition
Adverse Event (AE)	Any untoward medical occurrence in a participant to whom a medicinal product has been administered, including occurrences which are not necessarily caused by or related to that product.
Adverse Reaction (AR)	An untoward or unintended response in a participant to an investigational medicinal product which is related to any dose administered to that participant.

	The phrase "response to an investigational medicinal product" means that a causal relationship between a trial medication and an AE is at least a reasonable possibility i.e. the relationship cannot be ruled out.
	All cases judged by either the reporting medically qualified professional or the Sponsor as having a reasonable suspected causal relationship to the trial medication qualify as adverse reactions
Reference Safety	The RSI is a list of medical terms detailing the ARs that are expected for an
Information (RSI)	IMP and must be referred to when assessing a SAR for expectedness.
Serious Adverse Event (SAE)	 A serious adverse event is any untoward medical occurrence that: Results in death Is life-threatening* Requires inpatient hospitalisation or prolongation of existing hospitalisation Results in persistent or significant disability/incapacity Consists of a congenital anomaly or birth defect Other important medical events that jeopardise the participant or require intervention to prevent one of the above consequences * - life-threatening refers to an event in which the participant was at immediate risk of death at the time of the event; it does not refer to an event which hypothetically might have caused death if it were more severe.
Serious Adverse Reaction (SAR)	An adverse event that is both serious and, in the opinion of the reporting investigator, believed with reasonable probability to be due to one of the trial treatments, based upon the information provided.
Suspected Unexpected Serious Adverse Reaction (SUSAR)	A serious adverse reaction, the nature and severity of which is not consistent with the approved Reference Safety Information.

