5.1.2 Serious adverse events

A chronological listing of serious adverse events (SAEs) will be presented. The number of SAEs and the number of patients reporting at least one SAE will be reported.

Patient ID	Description	MedDRA Preferred Term	Severity	Relationship to treatment	Onset Date	Date of resolution	Duration	Seriousness criteria	Action taken in relation to SAE	Outcome

Version 1.0 [08/02/2024]

6 Statistical Software

Data will be output directly from MACRO into a STATA format by the NCTU at time-points agreed by the TMG. Statistical analyses will be carried out by the Trial Statistician at the PHSI BRG using Stata version 16. All programs and output will be stored in the School Statistics folder on the PHSI server.

7 Appendix: CTCAE grading relevant to MCDS-Therapy IMP DLTs

MedDRA Code	MedDRA SOC	CTCAE Term	Grade 1	Grade 2	Grade 3	Grade 4	Grade 5	Definition	
10002272	Blood and lymphatic system disorders	Anaemia	Haemoglobin (Hgb) <lln -="" 10.0="" <lln
- 6.2 mmol/L; <lln -
100 g/L</lln></lln>	Hgb <10.0 - 8.0 g/dL; <6.2 - 4.9 mmol/L; <100 - 80g/L	Hgb <8.0 g/dL; <4.9 mmol/L; <80 g/L; transfusion indicated	Life-threatening consequences; urgent intervention indicated	Death	A disorder characterized by a reduction in the amount of haemoglobin in 100 ml of blood. Signs and symptoms of anaemia may include pallor of the skin and mucous membranes, shortness of breath, palpitations of the heart, soft systolic murmurs, lethargy, and fatigability.	
1019491	Blood and lymphatic system disorders	Haemolysis	Laboratory evidence of haemolysis only (e.g., direct antiglobulin test; DAT; Coombs'; schistocytes; decreased haptoglobin)	Evidence of hemolysis and >=2 g decrease in haemoglobin	Transfusion or medical intervention indicated (e.g., steroids)	Life-threatening consequences; urgent intervention indicated	Death	A disorder characterized by laboratory test results that indicate widespread erythrocyte cell membrane destruction.	
10001551	Investigations	Alanine aminotransferase increased	>ULN - 3.0 x ULN if baseline was normal;	>3.0 - 5.0 x ULN if baseline was normal; >3.0 - 5.0	>5.0 - 20.0 x ULN if baseline was	>20.0 x ULN if baseline was normal; >20.0 x	-	A finding based on laboratory test results that indicate an	Also consider Hepatobiliary

[name]

	MCDS-Therapy	/	Statistical Analysis Plan Version 1.0 [08/02/2024]						

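### The adverse-reaction rows in SAP 5.1.1 leave out on-treatment events coded Not assessable, so they can be too low against the protocol's wording; the size cannot be estimated from the documents

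*SAP*

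**What the plan says.** SAP section 5 records the investigator's view of causality on six levels: "AEs are assessed for their relationship to treatment and coded as: Unrelated, Unlikely, Possible, Probable, Definitely, or Not assessable". SAP 5.1.1 then restricts the reaction summaries to "adverse reactions (those possibly, probably or definitely related to treatment", and both per-participant example tables (number of events, worst grade) repeat the three-level restriction in their row labels. Nothing in the SAP says what happens to a Not assessable event in those rows.

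Protocol 10.1 defines an adverse reaction in two steps. It first explains a response to the drug as one where "a causal relationship between a trial medication and an AE is at least a reasonable possibility i.e. the relationship cannot be ruled out". It then says that cases judged by the reporting professional or the sponsor "as having a reasonable suspected causal relationship to the trial medication qualify as adverse reactions". The protocol never mentions a Not assessable code.

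On scope, SAP section 5 states that "All AEs occurring from the point of consent to the end of trial participation are recorded in the trial MACRO database eCRF", and SAP 4.2 reports adverse events for everyone who starts the baseline period. Two listings are planned: "A line listing of all AEs will be reported, by participant, including severity, seriousness and relationship to study treatment", and "A chronological listing of serious adverse events (SAEs) will be presented", the latter with a relationship column.

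SAP section 5 grades severity from 1 to 5. The example worst-grade and organ-class tables have severity columns only up to Severe, which is the SAP's label for grade 3.

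**The concern.** A Not assessable code means that no causality judgement was reached, which differs from a judgement that the drug was unlikely to be responsible. By counting only three of the six levels, the SAP gives these events the same place in the reaction rows as Unrelated and Unlikely ones. They are also the events about which least is known.

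This matters because the trial has no control arm, and protocol section 5 describes the stage after dose-finding as a long-term assessment of safety as well as efficacy. The all-event rows cannot stand in for the reaction rows. Events are collected from consent, so the all-event rows mix treated time with a drug-free baseline of 12 to 18 months in Stage 1 and 6 months in Stage 2, and SAP 5.1.1 specifies no split by period. The organ-class table has no split by relationship. The reaction rows are thus the only planned adverse-event summary that separates possible drug effects from everything else, and the omission can move them in one direction only.

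**Working it through.** The plan states no figure to reproduce, so the check is mainly a comparison of texts.

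**1. Map the six codes (SAP section 5) onto the reaction rows (SAP 5.1.1).**

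| Code | In the reaction rows? | Judgement made? |
|---|---|---|
| Unrelated | No | Yes, against the drug |
| Unlikely | No | Yes, against the drug |
| Possible | Yes | Yes, towards the drug |
| Probable | Yes | Yes, towards the drug |
| Definitely | Yes | Yes, towards the drug |
| Not assessable | No, by default | No |

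**2. Compare with protocol 10.1.** The threshold of a reasonable possibility fits Possible, Probable and Definitely. The explanatory clause that follows it turns on whether a relationship has been excluded. For a Not assessable event it has not been. The two documents therefore do not clearly agree on this one code.

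**3. Look for another route to a judgement.** Protocol 10.4.2 has the Chief Investigator assign causality for serious events when a local assessment could not be obtained. It names no such route for non-serious events, so the code can persist there.

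**4. Restrict to treated time.** Protocol 10.1 ties a reaction to a dose that was given. A Not assessable event with onset before the first dose cannot be a reaction and must stay out of any inclusive count.

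**5. Form of the shortfall.** Let A be the number of events coded Possible, Probable or Definitely, and U the number of on-treatment events coded Not assessable. The largest relative shortfall in the event count is

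U / (A + U),

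reached only if every one of the U events is a reaction. The documents give neither A nor U. Purely as an illustration, with an assumed A = 20:

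- U = 0: 0/20 = 0%
- U = 2: 2/22 = 9%
- U = 5: 5/25 = 20%

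These show how the formula behaves; they are not estimates. If all 40 planned participants enter the summary, each such event moves the mean number of reactions per participant by 1/40 = 0.025.

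**6. Worst grade.** One event can change a child's category. A child with a mild Possible event and a severe Not assessable event is shown as Mild in the reaction row. If the severe event is the child's only candidate, the row shows None.

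**7. Where these events still appear.** They are in the all-event rows, the organ-class table, the count of patients with at least one event of grade 3, 4 or 5, and the listing of all events with relationship. If serious, they are also in the serious-event listing.

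**The case against.** The strongest counter-argument is that the SAP's three levels are a natural reading of the protocol. A reasonable possibility corresponds to Possible and above, and the next sentence of protocol 10.1 refers to cases that someone has judged to be suspected reactions. Not assessable is the absence of that judgement. Pressed to the letter, the explanatory clause might take in Unlikely events as well, which nobody proposes. This stands to the extent that a reader might infer that the protocol's definition plainly includes Not assessable events, and the documents do not establish that. What remains is an ambiguity that the SAP settles silently in the direction of fewer reactions.

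A second argument is that nothing is hidden: with 40 planned participants, a reader can count the code from the listing. That is true, and it rules out any reading that these events disappear from the safety report. It does not repair the summary rows, which are likely to be the figures quoted.

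A third is that safety and tolerability were the Stage 1 primary objective, already reviewed by the IDMC, and that safety reporting in this SAP is descriptive with no decision rule. That stands as a reason to treat the point as a modest one.

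On the grade columns, the tables are labelled as examples, the text promises the worst grade without a cap, and grades 3 to 5 are counted together. Fatal or life-threatening events also meet the protocol's seriousness criteria and would be listed individually. This largely answers the point, though not fully: the combined count is not restricted to reactions. The SAP appendix also assigns grade 4 to some laboratory values by threshold alone, and such a value need not be a serious event.

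**Conclusion.** The point holds in limited form. SAP 5.1.1 leaves on-treatment Not assessable events out of the adverse-reaction rows without saying so, and this does not clearly match protocol 10.1. The adverse-reaction count and worst grade can be too low and cannot be too high on this account.

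The size is unknown. It is zero if the code is never used after the first dose, and at most U/(A + U) otherwise. A reader might infer that drug reactions are in fact under-reported, or attach a percentage to the shortfall. The documents support neither, because they give no frequency for any causality code and do not say that an event that could not be assessed is a reaction. The conclusion rests on two things: reading the protocol's explanatory clause as at least capable of covering such events, and the absence of any SAP rule for the code.

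The missing grade 4 and 5 columns are a minor mismatch between example tables and the grading scale. They are not a gap in what is collected or listed.

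**What to change.** In SAP 5.1.1:

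- Add a separate line for events coded Not assessable with onset after the first dose.
- Report the adverse-reaction count and the worst adverse-reaction grade per participant twice, without and with those events. This avoids having to decide which reading of protocol 10.1 is correct and lets the reader see how much depends on it.
- Keep Not assessable events with onset before the first dose out of both versions.
- As a minor change, add grade 4 and grade 5 columns to the example worst-grade and organ-class tables so that they follow the grading in SAP section 5.

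The cost is a sentence or two of SAP text, one extra row and a recoding of variables already collected. The downside is a possibly less favourable adverse-reaction figure in the inclusive version.
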